**Investigational Agents:**

Drug Name:	Sodium Chloride
IND Number:	Not applicable
Sponsor:	Not applicable
Manufacturer:	Pine Pharmaceuticals

### **STATEMENT OF COMPLIANCE**

The trial will be carried out in accordance with International Conference on Harmonisation Good Clinical Practice (ICH GCP) and the following:

- United States (US) Code of Federal Regulations (CFR) applicable to clinical studies (45 CFR Part 46, 21 CFR Part 50, 21 CFR Part 56, 21 CFR Part 312, and/or 21 CFR Part 812)

National Institutes of Health (NIH)-funded investigators and clinical trial site staff who are responsible for the conduct, management, or oversight of NIH-funded clinical trials have completed Human Subjects Protection and ICH GCP Training.

The protocol, informed consent form(s), recruitment materials, and all participant materials will be submitted to the Institutional Review Board (IRB) for review and approval. Approval of both the protocol and the consent form must be obtained before any participant is enrolled. Any amendment to the protocol will require review and approval by the IRB before the changes are implemented to the study. In addition, all changes to the consent form will be IRB-approved; a determination will be made regarding whether a new consent needs to be obtained from participants who provided consent, using a previously approved consent form.

## 1 PROTOCOL SUMMARY

### 1.1 SYNOPSIS

[figure not shown]
Title:	Genomics, Environmental Factors and Social Determinants of Cardiovascular Disease in African Americans Study (GENE-FORECAST): Sodium Intervention Trial (SIT)/GENE-FORECAST SIT
Study Description:	The objective of this study is to implement a sodium intervention investigation to assess the effect of increased dietary sodium intake on changes in blood pressure, vascular function, microbiome, whole blood epigenome, whole blood and urine transcriptome as outcome measures. The study design will include a double-blind, cross-over treatment/placebo trial among 40 former African Americans GENE-FORECAST participants with normal blood pressure and will last 7weeks. It is hypothesized that exposure to increased dietary sodium will affect blood pressure, whole blood epigenome, whole blood and urine transcriptome, vascular function, microbiome and blood pressure.
Objectives:	Primary Objective: Define the effect of increased dietary sodium intake on microbiome and vascular function. Secondary Objective: 1) Determine if increased sodium affects blood pressure. 2) Determine if increased sodium affects whole blood epigenome. 3) Determine if increased sodium affects whole blood and urine transcriptome.
Endpoints:	Primary: Vascular function Microbiome Secondary: Blood pressure Whole blood epigenome Whole blood and urine transcriptome
Study Population:	Study population will include 40 former African American normotensive men and women ages 21-65 residing in the DC, Maryland, Virginia regions who previously participated in the GENE-FORECAST protocol.
Phase:	<0.
Description of Sites/Facilities	All protocol activities will take place at the NIH Clinical Center.
Enrolling Participants:	
Description of Study Intervention:	Participants will be enrolled in a double-blind cross-over sodium chloride/placebo intervention trial. Intervention product will be taken in capsule form (1 gram per capsule) 3 times per day.

**Study Duration:** Participants will be enrolled concurrently along with ongoing GENE-FORECAST protocol. It is anticipated that it will take 36 months from enrollment to completion of data analyses.

**Participant Duration:** It will take 7 weeks for each participant to complete 4 visits to the Clinical Center during the trial.

## 1.2 SCHEMA

**Figure 1: Randomized double-blind crossover treatment/control flowchart**

Participants will be randomized to a placebo or salt treatment arm for two weeks (Period 1), followed by a wash-out period for three-weeks, ending with a cross-over to the alternative treatment arm for two weeks (Period 2). The total length of participation is 7 weeks (Figure 1). Participants will be randomly assigned by a computer-generated code.

## 1.3 SCHEDULE OF ACTIVITIES (SOA)

It is estimated that participants will spend approximately 5 hours at the Clinical Center during baseline and approximately 3 hours during each of the subsequent visit. Obtaining and explaining the informed consent will take about 20-30 minutes. Administering the baseline questionnaires will take about 1.45 hours and 75 minutes for each subsequent visit. The clinic visit assessment, plus vascular function test, will take about 1.30 hours.

**Table 1: Estimated length of time for study procedures**

## GENE-FORECAST SIT

29JUL2024

NIH Clinic Visit	Estimated time 4 hours	Total Participants	Duration of Study
a) Informed consent (baseline only)	20-30 minutes	40	7 wks
b) Baseline Questionnaires	1.75 hours	40	Baseline
c) Phlebotomy	30 minutes	40	7 wks
d) Physical examination	20 minutes	40	7 wks
e) 24 diet recall	30 minutes	40	7wks
f) Microbiome	15 minutes	40	7 wks
g) Psychophysical Taste Task: Sucrose and Salt Detection Thresholds	30 minutes	40	7 wks
h) Psychophysical Taste Task: Sucrose and Salt Preference	20 minutes	40	7 wks
i) Vascular Function	1.0 hrs.	40	7 wks

**Visit to the NIH Clinical Center:**

Once potential participant arrives at the Clinical Center, they will report to admissions and be greeted by the GENE-FORECAST-SIT staff who will escort him/her to a private room to administer informed consent and baseline questionnaires. GENE-FORECAST-SIT staff (Research Nurse/Physician Assistant) will subsequently escort potential participant to phlebotomy followed by the collection of microbiome specimens from the GENE-FORECAST-SIT staff. A physical examination by the Physician Assistant will be performed on the participant, they will then have a standard physical exam, including blood pressure measurement and vitals concluding with administration of vascular function tests using Endo-PAT and SphygmoCor by the Physician Assistant. Two blood pressure measurements will be obtained from the participant by the Clinical Center Nursing Staff and an average recorded. The blood pressure will be measured using a Dinamap and will be obtained from the left arm after 5 minutes of rest with the participant in a sitting position with legs uncrossed. A 24-hour diet recall will be administered by staff from the Clinical Center Nutrition Department. Taste assessment will be administered by an Associate Investigator on the study.

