safe, intake in various cultures around the world. The increment in salt intake beyond the participant's usual diet is equivalent to eating 1-2 bowls of soup and is a dose commonly administered to treat orthostatic hypotension in patients who suffer from this disorder. It should be noted that the protocol focuses on normotensive volunteers and excludes patients with hypertension or heart failure for whom a transient increase in dietary sodium could pose a risk. We will assess, gut, skin and saliva microbiome. The oral cavity is an excellent source of easy-to-access biological material for studies of oral microbiome. This is due to the quick, non-invasive and low-cost collection. The most used source of oral samples is saliva (collected by passive drool or spit). The collection of the skin microbiome samples is commonly performed using the swabbing method. The sampling for skin microbiome was guided by the aim to consider two of the three skin microenvironments types: Sebaceous and moist microenvironments. For the first, the Retroarticular Crease was chosen and for the latter, the Antecubital Fossa was selected. These sites provide also the advantage of being relatively less exposed than dry sites such as the forearm and hence less likely to have the external environment microbiome over-represented.

The oral samples are not collected to investigate gut microbiome but rather to evaluate changes in oral microbiome with respect to changes in sodium intake. The aim is to find out if changes in sodium intake are correlated with microbiome changes in the oral cavity, in the gut and on the skin. Each site is considered separately first and then patterns of changes between sites are considered.

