7. Psychophysical Taste Task: Sucrose and Salt Preference: Sucrose and salt preference will be assessed using a two-series paired comparison-tracking method developed at the Monell Center for Adults. Subjects will be presented with pairs of solutions differing in sucrose concentration (3, 6, 12, 24, and 36 g per 100 mL) and salt (0.92–6.14% wt/vol NaCl). They will be asked to taste the solutions without swallowing and point to which of the pair they liked better. Subsequently, each pair presented will be determined by the subject's preceding preference choice. The entire task is then repeated with the stimulus pairs presented in reverse order. After completion of the taste task, the geometric mean of the sucrose concentrations chosen will be determined. This serves as an estimate of the participant's most preferred level of sucrose. The task takes approximately 15 minutes to complete.

8. Baecke's Physical Activity Questionnaire: Physical activity will be assessed using 16 questions involving three habitual physical activities (occupational physical activity, physical exercise, and leisure activities) during the previous 12 months.

9. Pittsburgh Sleep Quality Index (PSQI): This is a 19-item self-rated questionnaire for evaluating subjective sleep quality over the previous month.

10. Microbiome: Skin, saliva and stool samples will be collected by the GENE-FORECAST-SIT staff based on the utilization of Norgen kits. Participant will be swabbed in three locations of the skin and will spit in a prepared vial. Subjects will be required to not shower within 12 hours of sampling based on the guidelines from the NIH common fund Human Microbiome Project, an initiative to generate resources and facilitate the characterization of the human microbiota (Human Microbiome Project, *Nature*, 2012). Stool kits will be previously mailed to participant for collection and participant will give stool sample to GENE-FORECAST-SIT staff at the clinic appointment.

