### **8.2.2 Biospecimen Evaluations**

Participants will undergo standardized blood collection for chemistry panel, blood pressure measurement and vascular function test. Biological specimens will include peripheral venous blood collected by phlebotomy, urine, and stool. All biospecimens will be collected at the NIH Clinical Center which is in compliance with Clinical Laboratory Improvement Amendments

(CLIA). Blood, urine and stool samples will be collected from the Clinical Center by the GENE-FORECAST-SIT staff. The samples are brought to PI's lab by research study lab assistants where Laboratory Manager will prepare and store samples in freezers. Shipment of blood and microbiome samples for each visit per participant will be sent overnight for assay in dry ice in compliance with standard procedures. Each sample will be labelled with participant study ID.

Urine sample: (small quantity, 1 cup 90 ml)

1. Urine chemistries (e.g. sodium, chloride, potassium)
2. Urine creatinine and microalbumin (ACR)
3. Urine protein to creatinine ratio (PCR)
  1. Osmolality
  2. Urea Nitrogen
  3. Urine exosomes (RNA/microRNA)

Microbiome samples:

Stool/At home collection kit (quantity = 2 grams):

Skin: swab of inner elbow and behind ears

Oral: saliva

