**Microbiome:**

BODY SITE	SPECIMEN	COLLECTION TUBE
Oral Cavity	Saliva	Saliva DNA Collection, Preservation, and Isolation Kit
Skin	Retroauricular Crease (Left)	Swab Collection and DNA System
	Retroauricular Crease (Right)	
	Antecubital Fossa (Left)	
	Antecubital Fossa (Right)	
GI Tract	Stool	Norgen Stool Nucleic Acid Collection and Preservation System

Total volume of blood collected per visit = 87 ml, which is equivalent to about 5.8-6 tablespoons of blood.

Biological specimens collected from individuals will include peripheral venous blood and urine samples collected by phlebotomy. Oral microbiome samples will be acquired using a spit collection kit. Skin swabs will be used to obtain skin microbiome samples from the left and

right retroarticular crease, as well as, the left and right antecubital fossa. Stool microbiome samples will be collected in a stool kit mailed to participants prior to clinic visit. Detailed instructions for the preparation, handling, storage, and shipment of specimens will be explained in the study's MOP.

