#### 9.4.2 Analysis of the Primary Endpoints

The two primary endpoints are vascular function and microbiome.

First, vascular function difference between placebo and treatment (salt intake) will be estimated. Then, microbiome differential between treatment and placebo will be identified and estimate for each of the microbiome collection sides (skin, oral and gut). Details of the vascular function and microbiome analyses with respect to treatment and placebo are provided below.

Vascular function (e.g. pulse wave velocity, PWV) will be first analyzed as a continuous variable. Its relationship with salt intake will be investigated through multiple linear regression with vascular function as outcome and salt intake (a binary variable with two categories:

treatment and placebo) as exposure variable. For this analysis only samples with complete data for vascular function and salt intake will be considered. The outcome variable will be log transformed if it departs markedly from the Gaussian distribution. The aim of this first analysis is to estimate the effect of salt intake on vascular function. The effect size, p-value and 95% confidence interval will be provided as results.

The second endpoint is microbiome; the microbiome data of each of the all the collection sites (oral, gut and skins) will be analyzed separately. Prior to investigating the relationship between microbiome and salt intake, the raw microbiome data requires extensive processing and quality controls (QC) because of challenges posed by this type of data and the potential of spurious results if appropriate QC are not applied. The raw data will be processed in mainly 5 steps: (a) reads preparation (assembly of paired reads, filtering of low quality reads and identification of unique sequences), (b) Operational Taxonomic Units - OTU clustering (selection of unique OTU sequences), (c) quality controls (identification and removal of artifacts from amplicon reads, in OUT sequences). These tasks will be carried out using pipelines included in the standards operating protocols (SOPs) developed and used by the NIH Human Microbiome Project. For the metagenomic microbiome data, the *HUMANN2* pipeline will be used and for the 16s microbiome data the *DADA2* pipeline will be used.

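### The only described visit sequence puts the blood draw before the skin swabs, although the inner elbow is a skin site within a primary endpoint; swab first and record the arm used

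*Combined protocol and SAP*

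**What the plan says.** **Order.** Section 1.3 (Visit to the NIH Clinical Center) is the only narrative of how a visit runs. After consent and the baseline questionnaires, staff "will subsequently escort potential participant to phlebotomy followed by the collection of microbiome specimens". The physical examination and the vascular tests come later. No section gives the reverse order as a sequence.

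**Sites.** Section 8.2.2 lists "Skin: swab of inner elbow and behind ears". Its Microbiome part specifies four swabs: the left and "right retroarticular crease, as well as, the left and right antecubital fossa". The choice was deliberate. Section 4.2 wanted one sebaceous and one moist skin environment, and says that "the Retroarticular Crease was chosen and for the latter, the Antecubital Fossa was selected". It adds that these sites are less exposed, so outside organisms should be less prominent there.

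**Protection of the skin.** Section 8.2, item 10: "Subjects will be required to not shower within 12 hours of sampling". Nothing is said about antiseptic, dressings or the blood draw.

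**Role.** Section 9.4.2 states that "The two primary endpoints are vascular function and microbiome", and that the difference between treatment and placebo "will be identified and estimate for each of the microbiome collection sides (skin, oral and gut"). Table 2 schedules blood and skin samples at all four visits.

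**The concern.** The inner elbow is where blood is usually drawn, and the skin there is usually cleaned first. If so, one of the two chosen skin environments is wiped and punctured shortly before it is sampled. That works against the no-shower rule and against the reason given in Section 4.2 for choosing sheltered sites.

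What is at stake is the quality of one part of a primary endpoint. The microbiome model in Section 9.4.2 names treatment as its only covariate. It has no term for the punctured arm and no rule for combining left and right swabs. Disturbance from the draw would therefore go into unexplained variation. With at most 40 participants and many taxa tested under false discovery control, extra variation costs the ability to detect a real change.

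**Working it through.** No power or error-rate figure depends on this point, and the plan gives no figure to reproduce. The check sets the texts side by side and then counts swabs.

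**Step 1: is the order stated?** Yes, in Section 1.3, phlebotomy first. That text describes the baseline visit, since it refers to consent and baseline questionnaires. That Visits 2 to 4 run the same way is an inference.

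**Step 2: do the tables add anything?** Little. Both versions of Table 1 (Sections 1.3 and 8.2) list phlebotomy before microbiome, but they give durations, and their row orders differ. Table 2 lists the swabs before the blood sample. None of these is a sequence, so the point rests on the Section 1.3 narrative.

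**Step 3: do the two procedures meet on the same skin?** The swab site is explicit. The puncture site is not: Section 8.2.2 says only that the blood is peripheral venous. The stated 87 ml per visit makes a large arm vein plausible but does not prove it. No section names another vein, excludes the punctured arm or says to swab first.

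**Step 4: count exposed swabs.** Inputs: 4 skin swabs per visit, 2 of them antecubital (Section 8.2.2); 4 visits (Table 2); 28 participants enrolled (Section 12) or 40 planned (Section 9.2). All visits are taken as completed and the same order is taken to apply at each.

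| Assumed draw | Exposed per visit | 28 participants | 40 participants |
|---|---|---|---|
| Not at the inner elbow | 0 of 4 | 0 of 448 | 0 of 640 |
| One inner elbow | 1 of 4 | 112 of 448 | 160 of 640 |
| Both inner elbows | 2 of 4 | 224 of 448 | 320 of 640 |

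Totals: 4 × 4 × 28 = 448 and 4 × 4 × 40 = 640. One exposed swab per visit: 1 × 4 × 28 = 112 and 1 × 4 × 40 = 160, that is 25% of skin swabs and 50% of antecubital swabs. Two per visit: 2 × 4 × 28 = 224 and 2 × 4 × 40 = 320.

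The denominator is itself unsettled. Section 8.2, item 10, speaks of three skin locations, while Section 8.2.2 lists four.

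**Step 5: does it differ between salt and placebo?** Sequence is randomized and staff are blinded (Section 6.3), and the order of steps does not depend on assignment. If left and right swabs are pooled, one punctured arm gives the same exposed fraction (1 of 2) at Visit 2 and Visit 4, whichever arm is used. If same-side swabs are compared, a change of arm sets a disturbed site against an undisturbed one. With the arm chosen at random at each visit, this happens with probability 2 × 0.5 × 0.5 = 0.5; with one habitual arm it is 0. Neither case has a direction that favours salt or placebo.

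**The case against.** The strongest reply is that the mechanism is not in the documents: vein, arm, antiseptic and dressing are all unstated. Sections 8.2 and 8.2.2 leave procedural detail to a Manual of Operation that is not available here and may already deal with this. The narrative covers the baseline visit, whereas the salt-placebo contrast rests on Visits 2 and 4. On this view the matter belongs in the manual.

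Much of this stands. It limits confidence to moderate and makes the swab counts conditional. It does not remove the point. The protocol's only stated order is the unfavourable one, and a manual that reversed it would contradict Section 1.3, so that text needs correcting in either case.

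A reader might infer three stronger things, none of which the documents support:

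- **That the comparison of salt with placebo is biased.** The order is unrelated to assignment, so the expected harm is noise and not a systematic shift. The taxon tests also carry a Benjamini-Hochberg correction.
- **That punctured-arm swabs reflect antisepsis and carry no salt signal.** No skin preparation is described, and its effect on the sample cannot be sized from the documents.
- **That about half of participants have mismatched arms at Visits 2 and 4.** This needs random arm choice, which is undocumented, and it matters only for a same-side comparison, which Section 9.4.2 does not plan.

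**Conclusion.** The point holds as a sampling-order weakness of low to moderate severity. That phlebotomy comes first in the only visit narrative, that both inner elbows are swab sites, and that skin belongs to a primary endpoint are all explicit and uncontradicted. The central estimate of 1 of 4 skin swabs per visit rests on three assumptions: one antecubital puncture per visit, skin cleansing beforehand, and the baseline order being kept at later visits. Without the first it can range from 0 of 4 to 2 of 4.

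The consequence is lost precision at one arm of one skin subsite. The other elbow (in the one-arm case) and the retroauricular swabs are not directly affected, nor are saliva, stool or vascular function.

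**What to change.** 1. In Section 1.3 and the manual, place the skin swabs after consent and before phlebotomy, and state that this applies at all four visits.
2. Record the venipuncture arm and site at each visit.
3. Reconcile the number of skin locations between Section 8.2, item 10, and Section 8.2.2, and state in Section 9.4.2 how left and right swabs are combined.
4. Section 12 reports 28 participants already enrolled, and reordering cannot help samples already taken. For these, retrieve the arm where it was recorded and, before unblinding, pre-specify a sensitivity analysis that excludes antecubital swabs from the punctured arm. Keep the site in the main analysis. Where the arm is unknown, report how many swabs that concerns; do not discard the site by default.

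The cost is small. Two adjacent steps change places, and Table 1 allots 15 minutes to all microbiome collection, so the draw is delayed by no more than that. Past visits need a check of phlebotomy records, which may be incomplete, and one additional analysis.

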**Table 2: Specific activities by visit**

Activity	Visit 1 (baseline)	Visit 2 (after 2-week treatment)	Visit 3 (after 3-week washout)	Visit 4 (after second 2-week treatment)
24-Hour nutrient recall	x	x	x	x

Psychophysical Taste Task: Sucrose and Salt Detection Thresholds	x	x	x	x
Psychophysical Taste Task: Sucrose and Salt Preference	x	x	x	x
History and physical exam with medication history	x	x	x	x
Baeke's physical activity questionnaire	x			
Pittsburg sleep questionnaire	x			
Stool/skin/mouth swabs for microbiome analysis	x	x	x	x
Urine sample	x	x	x	x
Blood sample	x	x	x	x
Vascular function	x	x	x	x
24-hour blood pressure monitor given to participant	x		x	
24-hour blood pressure monitor returned by participant		x		x

